Biochemical Assessments:

Urine Toxicology: Rapid semi-quantitative ELISA urine drug screen test for morphine, oxycontin, methadone, buprenorphine, fentanyl, cocaine, amphetamine, methamphetamine, benzodiazepines, PCP and THC. Urine sample collection procedure has been described in a recent paper (Wang et al 2015).

Neuroimaging and cognitive: Overview of BOLD fMRI paradigms design: BOLD fMRI is a relative (non-absolute) measure, and experimental results are typically reported as contrast between conditions. Two main strategies are event-related and block designs (Aguirre et al 1999, Laurienti et al 2003).

Resting-state fMRI (rs-fMRI): During the 5-min rs-fMRI, participants will be instructed to stay awake, still, and to keep their eyes open. A fixation crosshair will be shown on a black background throughout the scan. No task performance will be required.

Visual Opioid Cue Task: Forty-eight drug-related and 48 control stimuli are presented randomly for 500 msec, separated by variable inter-trial intervals (ITI, 0–18 s). The stimuli sets are tailored to a specific pattern of OUD: prescription opioids only, heroin (IV and IN) only, and mixed prescription opioids and heroin (Shi 2016). The control stimuli that depict household objects and

chores are graphically and contextually matched to the drug-related stimuli (Langleben et al 2008, Wang et al 2015). Opiate craving is assessed with a subjective craving score (SCS), before and after each MRI session on a 0–9 Likert scale. There is no response requirement in the task, avoiding the possible confounds of individual differences in motor coordination/reaction time.

fMRI Go-NoGo task (GNG): The Go-NoGo fMRI task is a validated task testing cognitive control aspect of executive functions adopted from previous research (Goldman et al 2015). The Go stimuli included 122 positively valanced pictures (e.g. sweets), and the No-go stimuli were 38 negatively valanced pictures (e.g. snakes). Each trial consisted of a stimulus displayed for 300 ms, followed by 1700-ms baseline period during which a crosshair was displayed. Pseudo-random order of the stimuli and baseline periods was generated. Total Task Time: ~8 min. Our preliminary task performance data indicate that Go-NoGo task performance predicted XRNTX treatment failure ($p<0.01$). Performance will be coded by the number of errors of commission.

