6.3 Measures to Minimize Bias: Randomization and Blinding

Urn Randomization. We plan to use urn randomization to stratify subjects across the two treatment conditions. We will stratify subjects on sex on the day of randomization.

An off-site statistician will work with clinical research staff in setting up the urn randomization sequences and will ensure that the codes linking subject's ID numbers to treatments are secure. Randomization uses an electronic emergency-unmasking database in Microsoft Access accessible to the off-site statistician 24 hours a day.. Randomization tables are secured within Microsoft Access and are managed by an off-site statistician and data management study personnel, who do not work directly with study participants. The system only provides access for one subject at a time and all transactions are recorded. If a subject is prematurely discontinued from the trial, all attempts will be made to not break the blind. If an emergency necessitates that the blind be broken, only the off-site statistician will have access to the blind to do so. They will be given the name of the staff members who have authority to request that the blind be broken. The off-site statistician can be reached 24 hours a day and can access a subject's code rapidly.

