Visual Opioid Cue Task: Forty-eight drug-related and 48 control stimuli are presented randomly for 500 msec, separated by variable inter-trial intervals (ITI, 0–18 s). The stimuli sets are tailored to a specific pattern of OUD: prescription opioids only, heroin (IV and IN) only, and mixed prescription opioids and heroin (Shi 2016). The control stimuli that depict household objects and chores are graphically and contextually matched to the drug-related stimuli (Langleben et al 2008, Wang et al 2015). Opiate craving is assessed with a subjective craving score (SCS), before and after each MRI session on a 0–9 Likert scale. There is no response requirement in the task, avoiding the possible confounds of individual differences in motor coordination/reaction time.

fMRI Go-NoGo task (GNG): The Go-NoGo fMRI task is a validated task testing cognitive control aspect of executive functions adopted from previous research (Goldman et al 2015). The Go stimuli included 122 positively valanced pictures (e.g. sweets), and the No-go stimuli were 38 negatively valanced pictures (e.g. snakes). Each trial consisted of a stimulus displayed for 300 ms, followed by 1700-ms baseline period during which a crosshair was displayed. Pseudo-random order of the stimuli and baseline periods was generated. Total Task Time: ~8 min. Our preliminary task performance data indicate that Go-NoGo task performance predicted XRNTX treatment failure ($p<0.01$). Performance will be coded by the number of errors of commission.

MRI Image Acquisition: Neuroimaging will be performed on a 3-Tesla Siemens Prisma scanner equipped with a 64-channel head coil. Prior to scanning, participants review instructions and practice all fMRI tasks. An MR-compatible button-box is used to record task responses (Current Designs, Philadelphia, PA). A T1-weighted multi-echo magnetization-prepared, rapid acquisition gradient echo (MPRAGE) structural image is acquired using standard parameters at 1-mm

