fMRI Image Processing will utilize standard image processing procedures (Langleben et al 2008, Langleben et al 2014, Wang et al 2015). Briefly, functional image analysis will utilize FSL platform (Functional MRI of the Brain Software Library) (Jenkinson et al 2012) and will include: B0 correction using FUGUE; slice time correction, motion correction (Jenkinson et al 2002), high-pass filter (120 sec), spatially smoothing (6 mm FWHM, isotropic) and mean-based intensity normalization. Resulting translational motion parameters will be examined to ensure that there is not excessive motion (i.e. >3 mm in any plane) and will be included in the General Linear Model (GLM). BET is used to remove non-brain areas (Smith 2002). Subject-level time-series statistical analysis will be executed with FSL's improved linear model (Woolrich et al 2001). Contrasts of interest are: drug vs. control stimuli (Cue Task); No-Go vs. Go (GNG); correct vs. incorrect No-Go (GNG). Preprocessed rs-fMRI data will undergo linear de-trending, band-pass filtering (.01–.08 Hz), and regression of confound variables (motion parameters, white matter/cerebrospinal fluid signals). The bilateral NAcc will serve as the seed region, and the connectivity with the NAcc will be indexed by the Fisher-transformed correlation coefficients between the time series of the NAcc and other brain regions as defined by the Power nodes (Power et al 2011). Subject level statistical maps will be co-registered to the T1 image using boundary-based registration (Greve et al 2009) and normalized to the MNI 2mm template using a highly accurate, deformable registration via attribute matching and mutual-saliency weighting (DRAMMS) (Ou et al 2011). Given our strong *apriori* hypotheses based on preliminary data and current literature, we will utilize a combination of hypothesis-driven regional analyses as well as follow-up whole-brain voxel-wise analyses.

Hypothesis-driven regional analyses: For each subject, regions of interest (see H1a) will be defined anatomically using the Harvard-Oxford Probabilistic Atlas (Hayasaka et al 2003) as well as by using in-house templates. For regional analyses, the signal to noise ratio will be maximized by averaging voxels within the region prior to extraction of mean percent signal change for entry to a hypothesis-specific statistical model as detailed in section C5.

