9 STATISTICAL CONSIDERATIONS

9.1 Statistical Hypotheses

Overview of primary hypotheses: Our primary response will be a binary indicator of treatment failure on the XRNTX or XRBUP regimen, defined as ≥ 2 weekly UDS positive for opioids, or self-report of ≥ 2 periods of three or more days of opioid use, or refusing XRNTX or XRBUP, or dropping out of study entirely. In hypotheses H1a and H1b, we are examining the effects of small, pre-specified, sets of measures, so our analyses will focus on model fit and prediction, and not on model selection. In hypothesis H1c, we search for best sets of predictors among demographic and clinical-behavioral variables, and over sets of brain/neural measures, so our focus is on model selection and on avoiding overfitting to the available data.

R61 Phase:

Hypothesis H1 (fMRI): For each of the cue reactivity (H1a), response inhibition (H1b), and connectivity (H1c) brain measured, we have a small number of neural responses associated with one or two regions of interest. These variables are continuously distributed, so we will test Hypotheses 1a, 1b and 1c using a repeated measures analysis of variance (rm-anova). The models will include a within-subject factor for Session (PRE vs ON) and a between-subject factor Group (XRNTX vs XRBUP), and their interaction. To accommodate the anticipated non-normal distributions of the response, we will use a generalized estimating equation (GEE) approach, using robust standard errors, using a compound symmetry working correlation structure for the within-subject correlations between the PRE and ON fMRI scans (Diggle PJ et al 2002). We will perform the rm-anova separately for each ROI (mPFC and VS for H1a, IFC for H1b, and VS-rtIFG and VS-mPFC for H1c). The hypotheses will be addressed by the Session by Group interaction, and we will obtain estimates and standard errors of the PRE vs ON change within each of the two groups, along with the size, standard error and significance of the differences between these estimates.

Sample size considerations for sample: The sample size is adequate for application of the GEE methods to obtain robust standard error (Lipsitz et al 1994). For a test of the PRE vs ON effect, our sample yields 80% power for a one-sided test that the ON levels will be Cohen's $d=0.4$ lower than the PRE levels, consistent with a decrease of Cohen's $d=0.5$ observed in our preliminary data and a decrease of Cohen's $d=0.3$ in the Suboxone sample.

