Milestone for transition from Phase 1 to Phase 2: Using the models described above, we will obtain (model-based) estimates of the Session (PRE vs ON) by Group (XRNTX vs XRBUP) effects for the five hypotheses described above. If these estimates show at least small effects (Cohen's $d \geq 0.2$) in at least two of the three domains, then we will continue to the R33 phase.

Primary Analyses for Phase 2: Session by Group interaction effects on neural response: First, we will formally test the interaction effects explored in the R61 phase. We will rerun the analyses described for H1a, H1b and H1c in the R61 phase, for the full sample of $n=140$ obtained through the R61 and R33 phases. The models will be exactly as described in the R61 phase.

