Effects of neural response on relapse vulnerability: Our primary outcome combines adherence to treatment and frequency of illicit opioid use during treatment. The primary outcome is a binary indicator of treatment success: if a patient provides ≥ 2 weekly UDS positive for opioids, or self-report of \geq two or more periods of ≥ 3 days of opioid use, or refuses XRNTX or XRBUP, or drops out of treatment entirely, then they will be classified as a treatment failure; otherwise they will be classified as a treatment success. We will calculate the PRE-ON change in %-signal-change for each of the regions and neural responses described in the R61 phase. We will use logistic regression models to predict the log-odds of treatment success (Aitkin et al 2009). The predictors in the model will be a binary factor for Group (XRNTX vs. XRBUP), and the neural change scores. We anticipate that there will be some greater PRE to ON changes in the XRNTX group than in the XRBUP group, so there will be some confounding between the effects of change score and the effects of Group on the rates of positive UDS. Thus, we will include Group first in our model, so evaluating the Group effect separate from the change-score effects, and then include the change scores in a model including Group, so evaluating the additional effect of change-scores in addition to the existing effects of Group. To assess whether the effects of the change scores differ between the XRNTX and XRBUP groups, we will also test for interaction effects between Group and each of the change-scores, by adding the interaction terms to the model that includes the group and neural change score main effects. We will check the assumptions underlying the logistic regression models (e.g. linearity of covariates effects on log-odds, outliers, influential observations) using standardized residuals, influence diagnostics, and graphical displays.

Sample size considerations for the sample: Analyses of Session by Group effects on neural response: For a one-sided test that the PRE vs ON effect is larger in the XRNTX group than in the XRBUP group, our sample of 70 per group yields 81% power for an effect of $d=0.42$ or greater. This effect is similar to the effects observed in the preliminary data. On the basis of the preliminary data we anticipate Group by Session effects of approximately $d=0.38$ in the VS and $d=0.42$ in the mOFC.

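### Cue-task pictures follow each participant's opioid pattern, but no specified relapse model contains set or pattern, so either may confound the link between cue-related brain change and treatment failure

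*Combined protocol and SAP*

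**What the plan says.** Section 6.1 (Visual Opioid Cue Task), repeated in section 8, states: "The stimuli sets are tailored to a specific pattern of OUD: prescription opioids only, heroin (IV and IN) only, and mixed prescription opioids and heroin". The household control pictures "are graphically and contextually matched to the drug-related stimuli", so the matching described is between drug and control pictures. Nothing is said about equivalence across the three sets, or about whether a participant sees the same set at both scans.

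The models are in section 9.1:

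- **H1a** (mPFC and VS): "The models will include a within-subject factor for Session (PRE vs ON) and a between-subject factor Group (XRNTX vs XRBUP), and their interaction". For Phase 2, "The models will be exactly as described in the R61 phase".
- **H2a** (treatment success or failure): "The predictors in the model will be a binary factor for Group (XRNTX vs. XRBUP), and the neural change scores". Group-by-change interactions are then added.
- **H2b** (Predictive modeling): the demographic search covers age, race, gender and education. The clinical search covers depression, anxiety, withdrawal, craving and the ASI composites. Neural change is searched last.

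Section 9.4.1 allows further covariates to be considered for the precision of treatment effects and names only prior cocaine use. On allocation, section 6.3 says: "We will stratify subjects on sex on the day of randomization".

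**The concern.** In H2a the predictor is a brain change score and the outcome is treatment failure. Participants are randomised to medication, not to brain change, so any baseline factor related to both can create an association. Opioid pattern is a candidate that the task itself brings in: it decides which pictures generate the mPFC and VS scores, and it is a pre-treatment characteristic that could bear on failure. Section 9.1 already accepts this logic for treatment arm. It expects Group and change scores to be confounded and enters Group first for that reason. It makes no such provision for picture set.

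The claim at stake is that brain signal explains treatment failure (H2a) and adds to demographic and clinical predictors (H2b). If pattern is missing from the H2b baseline model, a cue score that partly reflects pattern could earn a gain in AUC that is then credited to the brain measure.

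**Working it through.** **1. The plan's own figures.** Section 9.1 gives 81% power for 70 per group at d = 0.42, one-sided. No alpha is stated. At 0.05, the noncentral t with noncentrality 0.42 × √(70/2) = 2.485 and 138 df gives 79.6% (80.0% by the normal formula), so the figure reproduces. Section 9.2 attaches the same 81% to 80 per group, which computes to 84.4%; that mismatch needs reconciling but does not affect this point. For H2a the plan claims 80% power for an odds ratio of 1.75 per SD. The standard formula n·p(1−p) = (1.960 + 0.842)² / (ln 1.75)² with n = 140 gives p(1−p) = 0.179, an outcome proportion of about 0.23. The documents do not state that proportion.

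**2. H2a with no true brain effect.** Take two picture sets with shares q and 1−q, cue change differing by δ within-set SDs, and outcome odds differing by a factor R. To first order, the unadjusted log odds ratio per SD of cue change is

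b = ln(R) · δ · q(1−q) / √(1 + δ²·q(1−q)).

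Its standard error is about 1/√(n·p(1−p)). With n = 140 and an assumed outcome proportion of 0.4, that is 1/√33.6 = 1/5.80. For δ = 0.8, R = 3 and q = 0.5:

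- b = 1.0986 × 0.8 × 0.25 / √1.16 = 0.204, an odds ratio of 1.23.
- z = 0.204 × 5.80 = 1.18.
- Two-sided 5% rejection rate = P(Z > 0.78) + P(Z < −3.14) ≈ 22%.

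Simulations (n = 140, Group odds ratio 1.25) agree with the formula:

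| Split | δ | R | Odds ratio, formula | Rejection, formula | Rejection, simulated |
|---|---|---|---|---|---|
| 50/50 | 0.2 | 2 | 1.04 | 5.5% | 4-6% |
| 50/50 | 0.5 | 2 | 1.09 | 8% | 7-8% |
| 50/50 | 0.5 | 3 | 1.14 | 12% | 9-13% |
| 50/50 | 0.8 | 3 | 1.23 | 22% | 19-21% |
| 80/20 | 0.8 | 3 | 1.14 | 12% | about 11% |
| 90/10 | 0.8 | 3 | 1.08 | 7% | about 6% |

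At the outcome proportion implied by the plan's own power figure (p(1−p) = 0.179), the 50/50, 0.8 SD, threefold case becomes z = 0.204 × √(140 × 0.179) = 1.02, a rate of about 17-18%.

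With set in the model, the odds ratio returns to about 1.00 and the rate to about 5%.

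**3. Three equal sets.** If set explains 2% of change variance and the success odds differ 1.5-fold per step, the odds ratio is 1.04 and the rate 5.4%. At 10% and twofold per step they are 1.20 and 15.6%. An extreme case, 20% and twofold per step (so fourfold between the outer sets), gives 1.29 and 27%; the conclusion does not rest on it. If set is unrelated to change, or unrelated to outcome, the rate is 4.4-4.8%.

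**4. H1a.** The test concerns within-person change in a drug-minus-control contrast. A set effect that is equal at PRE and ON subtracts out; simulated power stays at about 80% with no bias. Only set differences in change matter. If they make up a share r of change variance, adjustment replaces d by 0.42/√(1−r). Power goes from 79.6% to 80.3%, 81.4% and 83.2% for r = 2%, 5% and 10%, a gain of 0.7 to 3.6 points.

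**The case against.** The strongest objection is that the bias is hypothetical. It needs set or pattern to relate both to cue change and to failure, and the documents report neither. That stands, and is why the point says may. The size also depends on the split: about 21% needs a 0.8 SD difference, threefold odds and an even split together, and smaller effects or an uneven split bring the rate close to nominal.

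Second, only two of the five neural measures come from the cue task, and the plan stages its adjustment: H2a takes brain response alone, and H2b then adds demographic and clinical variables, including ASI composites that cover drug use. The demographic list is not closed. This helps in part, but no listed predictor is opioid type or picture set, and the covariate clause in section 9.4.1 is aimed at treatment effects rather than at the brain-outcome association.

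A reader might go further and infer that mixing sets necessarily adds noise to H1a, or that chance imbalance of sets between arms biases it. The documents do not support this. A constant set effect cancels, randomisation keeps the test unbiased, and chance imbalance is already reflected in the unadjusted standard error. It follows that opioid pattern does not need to become a second urn factor.

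**Conclusion.** The concern holds for H2a and H2b in conditional form. Picture set is tied to opioid pattern, no specified relapse model contains either, and randomisation does not protect the association being tested. Under the assumed effects the spurious odds ratio per SD is about 1.04 to 1.23, with a false-positive rate from about 5-6% up to about 21%. Even the upper odds ratio is well below the 1.75 that the plan is powered to detect, so the risk is a false or inflated modest association rather than a large one.

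The stronger statement, that set does confound the relapse analysis, goes beyond the documents, which contain no data on either link. The size rests on assumed set differences, outcome odds ratios, pattern shares and a 40% outcome proportion. H1a has at most a small, conditional loss of precision and no bias.

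**What to change.** Before analysis, amend the SAP as follows:

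- **H2a:** prespecify cue set (equivalently opioid pattern, three levels) as a covariate in every model that uses the mPFC or VS cue change score, with a rule for combining sparse levels.
- **H2b:** put it among the baseline demographic and clinical predictors, so that it is in the model before brain measures are added.
- **Interpretation:** state that adjustment cannot separate picture version from opioid type, because each pattern sees only its own set. Either is an alternative explanation to brain signal, and adjustment deals with both together.
- **Recording:** list set as a baseline variable and state whether it is the same at both scans. It must be known to run the task, but the Schedule of Activities does not show it.
- **H1a (optional):** add set and Session by set as precision terms. With three levels this is 2 + 2 = 4 extra parameters in the repeated-measures model.

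The cost is two degrees of freedom per relapse model and minor analysis work. The randomisation does not change.

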XRBUP (CAM2038, Brixadi) is a subcutaneous (SC) injectable extended-release formulation of buprenorphine that has been developed by Camurus AB (Sweden) and licensed in the US by Braeburn Pharmaceuticals. Brixadi is available in a range of weekly and monthly doses (8,16,24 and 32 mg weekly and 64 and 96 mg monthly) (Lofwall et al 2018). CAM2038 was approved under brand name Buvidal for OUD by the European Medicines Agency and approved as Brixadi by the FDA. This creates a unique window of opportunity for research. Braeburn, the US licensee of Brixadi has agreed to provide the study medication at no cost (See Letter of support).

XRNTX (Vivitrol): is a monthly extended-release intramuscular injection of 380 mg of naltrexone manufactured by Alkermes Inc, that has been approved by the FDA for OUD since 2010 (Lee et al 2017) XRNTX maintains therapeutic levels of naltrexone and its active metabolites for approximately 4 weeks after each injection.

Functional magnetic resonance imaging (fMRI): is an established method of clinical medical imaging. Combined with **neurocognitive testing**, standard clinical MRI scanner can be used as an accurate and robust means of evaluation of brain response to medications such as opioid agonists and antagonists, that modulate cognitive and motivational processes in addiction (Davis et al 2017, Moningka et al 2019).

Neurocognitive testing: Psychological tasks are a well-established means to evaluate a particular cognitive or emotional domain. We shall use established tasks probing four domains: motivation, response inhibition, emotional controls and awake rest during the fMRI sessions, to simultaneously assess domain-specific behavioral performance and brain activity.

Group (XRNTX, XRBUP) by Session (PRE, ON) **interaction** in the brain fMRI signal in 4 cognitive domains

**Primary
Endpoint:**

Domain-specific cognitive performance, Urine toxicology, Adherence to follow up and treatment visits.

**Secondary
Endpoints:**

**Study
Population:**

200 individuals between the ages of 18 and 65 who have a diagnosis of Opioid Use Disorder (OUD).

Phase:

Phase 2a/b

**Description of
Sites/Facilities**

UPenn Department of Psychiatry, Center for the Study of Addictions, [name]

**Enrolling
Participants:**

UPenn Center for the Study of Addictions

Description of Study Intervention: XRBUP (CAM2038) or XRNTX (Vivitrol)

Study Duration: Six years (72 months)

Participant Duration: 20 weeks

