Daytime sedation is uncommon and usually temporary. If it persists, patient will be interviewed again about concomitant sedative medications or alcohol. If these or other unrelated causes such as insomnia are not identified, the PI will determine whether it is necessary to exclude the participants from the study.

Meticulous injection technique: our experienced personnel who has administered thousands of Vivitrol injections without ANY complications over a decade, psychoeducation

Applying the exclusion criterion regarding elevated liver function tests labs described in the Exclusion Criteria section above.

Opioid overdose is a feared complication of OUD in general. In the context of the present study, overdose needs to be considered in two settings: during treatment and after participation ended. Individuals receiving buprenorphine or naltrexone are unlikely to experience opioid overdose during treatment, because buprenorphine is a partial agonist whose antagonist properties increase in a dose-dependent fashion and naltrexone is an antagonist that blocks the effects of illicit opioids. Buprenorphine treatment discontinuation does not lead to precipitous increase in sensitivity to illicit opioids. Individuals formerly treated with XRNTX do lose their tolerance to opioids and are therefore at an increased risk of opioid overdose if they discontinue MAT

treatment abruptly and usually against medical advice. Nevertheless, studies found that the rate of opioid overdoses after XRNTX discontinuation is actually lower than in the control groups. However, to minimize the risk of overdose, participants completing the study will be referred to the clinical program of their choice using a “warm-handoff” procedure that will include (1) beginning to make arrangements for post-study referral before the effects of XRNTX or XRBUP wear off allowing one month for the project coordinator and the participant to establish clinical treatment (2) monitoring and assisting participants in making their follow up appointment and escorting them to their first appointment as needed (3) Providing psycho-education about opioid overdose risk and provide prescriptions for the nasal Naloxone spray used as a rescue in case of an overdose.

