Aim 1 (Phase 1): Estimate the differential brain fMRI response between XRNTX and XRBUP in OUD treatment groups. We hypothesize that (**H1**) XRBUP and XRNTX will modulate the regional brain activity in the two-key cognitive-behavioral domains and measures of brain connectivity from pre-treatment (PRE) to on-treatment (ON) and this response will differ between the two medications. Milestone for transition to Phase 2: The MAT group (XRNTX, XRBUP) by Session (PRE, ON) **interaction** will have at least small ($d' \geq 0.2$) effect size in all brain measures.

H1a: Incentive salience (opioid cue-reactivity task): The decrease in the brain response to drug related stimuli (ON minus PRE) in the medial prefrontal cortex (mPFC) and the ventral striatum (VS) will be **greater** in the XRNTX than in the XRBUP group.

H1b: Executive function (Go-NoGo task): XRNTX will improve the efficiency of response inhibition more than XRBUP, leading to a greater **decrease** in the brain signal (ON vs PRE) during the NoGo trials in the inferior frontal cortex in the XRNTX group (see A.2.b).

H1c: Resting state functional connectivity (rsFC): change (ON vs PRE) in the rsFC between the VS and the right inferior frontal gyrus (rtIFG) and the mPFC will be **greater** in the XRNTX (vs. XRBUP group).

Aim 2 (Phase 2): Confirm in the full sample (n=200), the significance of MAT (XRNTX, XRBUP) by Session (PRE, ON) interaction in all domains from Aim 1. Test the explanatory value of integrated brain-behavior models of relapse vulnerability, identify differences in variable loading between MAT group, and explore potential mechanism of individual variability in treatment outcome.

H2a: Using logistic regression, we will test the explanatory value of brain signal in modeling treatment failure (Section **C.5.c**) and identify specific variables that differentiate MAT groups (interaction).

H2b (Exploratory): Test if the models that include brain response better explain treatment success or failure when compared to those fitted solely with demographic and clinical measures: demographic + clinical measures vs. demographic + clinical measures + brain response).

3.3 Secondary Study Endpoints (abbreviations spelled out on Page 27, “STUDY MEASURES”):

Depression (HAM-D2); Anxiety (HAM-A); Opioid Withdrawal (COWS); Opioid Craving (Opioid Craving Scale); TLFB interview; Percent UDS positive for cocaine (Ten-drug urine screen)

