13 APPENDIX

13.1 Schedule of Activities (SoA)

	Screening detox and randomization (Day -14)	MRI Scan 1 Baseline (day 0)	Induction to XRBUP or XRNTX (day 0-10)	Injection 1 (day 10) + weekly follow up	Injection 2 (day 40)	MRI Scan 2 On Treatment (day 55)	Injection 3 (Day 70)	Weekly Follow- up End of study and referral (Day 100)
Psychiatric and medical								
Demographics (age ¹ , sex ¹ , edu ¹)		X						
History, physical and labs (C.4.a)		X						
SILS		X						
MINI (EOS* – end of study)		X						X EOS*
Addiction Severity Index ¹		X						X EOS*
Clinical/Behavioral (C.3.a)								
HAM-D ² , HAM-A ² , COWS ²	X	X	X		X	X		X
SOWS, Opioid Craving Scale ² , SF-MPQ-2 ² , STAI-6		X	X	X	X	X		X
TLFB interview	X	X	X		X	X		X
Ten-drug urine drug screen (UDS)	X	X	X	X	X	X		X
Go-NoGo errors of commission ²		X		X				
Neuroimaging (Section C.3.b)								
Go-NoGo fMRI ³		X			X			
Opioid Cue task fMRI ³		X			X			
Resting-state fMRI ³		X			X			
MPRAGE (anatomical MRI scan)		X			X			

PRINCIPAL INVESTIGATOR SIGNATURE

STUDY SPONSOR: [name]

STUDY TITLE: **Open label comparison of injectable extended release preparations of buprenorphine (Brixadi®) and naltrexone (Vivitrol®) for the treatment of opioid use disorder**

STUDY ID 843403

PROTOCOL VERSION V5.0

I have read the referenced protocol. I agree to conduct the study in accordance to this protocol, in compliance with the Declaration of Helsinki, Good Clinical Practices (GCP), and all applicable regulatory requirements and guidelines.

Principal Investigator Name	[name]	Signature
Affiliation:	University of Pennsylvania	Date 7/17/2023

END OF DOCUMENT

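### Go-NoGo performance is scored by commission errors alone, so a participant who never responds gets the best possible score, and no Go-accuracy rule catches it

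*Combined protocol and SAP*

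**What the plan says.** The task has 122 Go and 38 No-Go pictures (section 6.1, fMRI Go-NoGo task). Its scoring rule reads: "Performance will be coded by the number of errors of commission". Section 8 repeats the rule. The Schedule of Activities (section 13.1) has one behavioural row for the task, "Go-NoGo errors of commission".

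For this task neither section mentions Go hits, omissions, reaction time, a minimum response rate or a check that the participant was awake. The only scan-quality check in the image-processing text of section 8 is head motion above 3 mm. By contrast, the face-emotion task in section 6.1 is scored on accuracy and correct reaction time.

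The score falls under the synopsis secondary endpoints: "Domain-specific cognitive performance, Urine toxicology, Adherence to follow up and treatment visits". It also bears on H1b (Aim 1, section 3.2), which states that "XRNTX will improve the efficiency of response inhibition more than XRBUP" and predicts a larger fall in inferior frontal signal on XRNTX.

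On sedation, section 2.2.1 describes over-sedation with buprenorphine as rare. The XRBUP risk text in section 2.3.1 adds: "Daytime sedation is uncommon and usually temporary".

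**The concern.** The score is meant to measure response inhibition, but it uses only the 38 trials on which the right action is to do nothing. Withholding a press through control and failing to press through inattention give the same record. The 122 Go trials, which would tell them apart, do not enter the score.

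Two things are at stake. First, a run in which the task was not performed enters the secondary endpoint as perfect performance. Second, H1b reads a fall in frontal signal as greater efficiency. Disengagement could plausibly lower that signal too, and behaviour is the natural way to separate the two. A commission count alone cannot do so.

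Lapses might also differ between sessions. The PRE scan follows detoxification, and section 2.3.1 lists over-sedation among the common side effects of the withdrawal medicines. Randomisation comes after abstinence is reached (section 6.1), so this bears on PRE-to-ON change more than on an arm difference at PRE.

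**Working it through.** The documents give no error rate, lapse rate, power or alpha for this score, so there is no stated figure to reproduce. The check is what the rule returns for given behaviour.

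**Inputs from the documents:** 122 Go and 38 No-Go trials, 160 in all (section 6.1).

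**Assumptions:** attentive false-press rate FA = 0.10 to 0.40; attentive Go hit rate H = 0.95; a share L of trials gets no response, at random.

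**Step 1, the extreme case.** No model is needed. With no presses, commission errors are 0 of 38 and Go omissions are 122 of 122. Only the 38 No-Go trials are correct: 38/160 = 23.8%.

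**Step 2, partial lapses.**
- Commission errors = 38 × FA × (1 − L)
- Go omissions = 122 × (1 − H × (1 − L))
- d-prime = z((Go hits + 0.5)/123) − z((commission errors + 0.5)/39)

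At FA = 0.20:

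| L | Commission errors | Go omissions | d-prime |
|---|---|---|---|
| 0 | 7.6 | 6.1 | 2.42 |
| 0.2 | 6.1 | 29.3 | 1.66 |
| 0.3 | 5.3 | 40.9 | 1.46 |
| 1.0 | 0 | 122 | −0.42 |

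The planned score improves down the table while omissions and d-prime worsen. The direction is the same across the range: with L going from 0 to 0.3, the count falls from 3.8 to 2.7 at FA = 0.10 and from 15.2 to 10.6 at FA = 0.40.

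**Step 3, size of a between-arm bias if sedation is uncommon.** Assume equal true inhibition, mean false-press rate m = 0.10 to 0.30, and between-person SD s = 0.08 to 0.12. A fraction f of one arm lapses on 30% of trials.
- Shift in the arm mean = 38 × m × 0.30 × f
- SD of the count = √(38 × m × (1 − m) + 38 × 37 × s²), for participants who do not lapse

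Example with m = 0.20, s = 0.08: SD = √(6.08 + 9.00) = 3.88. For f = 0.05 the shift is 0.114 and d = 0.03. For f = 0.10 the shift is 0.228 and d = 0.06.

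Smallest case, m = 0.10, s = 0.12, SD = 4.86: d = 0.057/4.86 = 0.01 (f = 0.05) and 0.114/4.86 = 0.02 (f = 0.10). Largest case, m = 0.30, s = 0.08, SD = 4.12: d = 0.171/4.12 = 0.04 and 0.342/4.12 = 0.08. The range is therefore 0.01 to 0.04 at 5% and 0.02 to 0.08 at 10%.

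**Step 4, would d-prime be a safer main score?** Take the same m and s, an attentive Go hit rate of 0.90 to 0.95 with between-person SD 0.03 to 0.08 (assumed), and an excess lapse rate of 10% across a whole arm. By simulation, the spurious difference is about d = 0.1 to 0.3 on the count and about 0.5 to 1.3 on d-prime, in the opposite direction.

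**The case against.** The strongest reply is that no specified analysis is shown to be biased. H1b is decided by the Group by Session interaction in frontal signal (section 9.1), and commission errors do not enter that model. Section 9 names no between-arm test of the count. The secondary endpoint list in section 3.3 omits it, so only the synopsis phrase covers it. All of this stands, and it limits the point to a secondary behavioural measure. It does not make the rule sound, because the rule is stated and returns the best value for a run that was not performed.

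Four stronger readings are tempting, and the documents do not support them.

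- *Sedation could falsely support H1b.* Among the two study drugs, the documents attach sedation only to buprenorphine; the naltrexone risk list in section 2.3.1 omits it. Fewer counted errors would flatter XRBUP, which works against H1b.
- *The bias is comparable to the effects the plan powers for.* A 30% excess lapse rate across an entire arm would give d of about 0.3 to 0.9, but that does not fit an effect described as rare or uncommon. The plan's d = 0.2 and d = 0.42 also refer to the neural interaction, not to this count.
- *Any drowsy participant looks near-perfect.* Only a complete non-responder does. Partial lapses lower the count in proportion, and drowsiness that weakens inhibition itself could raise it.
- *The count should be replaced by d-prime.* Step 4 shows that d-prime is more affected by lapses. If XRBUP were the sedated arm, its error would favour H1b.

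**Conclusion.** The point holds as a scoring defect. Commission errors alone cannot separate inhibition from non-response, and a participant who does nothing receives the best value on part of a secondary endpoint. This follows from the definition and needs no assumption.

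The size of any between-arm bias cannot be computed from the documents. Under the random-lapse model, with 5-10% of one arm lapsing on 30% of trials, it is about d = 0.01 to 0.08. All the rates behind that range are assumed. The primary H1b test is not affected through this score. The change is still worth making because it costs little and has to be fixed before the data are seen.

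**What to change.** In the Go-NoGo paragraphs of sections 6.1 and 8, and in section 9:

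- Keep the commission-error count as the behavioural score.
- Report the Go omission rate by arm and session beside it.
- Set, before data review, a minimum Go hit rate below which the behavioural run is treated as non-performed and therefore missing. The documents give no hit rates, so the team should choose the value from its own task experience.
- Report the number of flagged runs by arm.
- Repeat the Go-NoGo fMRI analysis without flagged runs as a sensitivity analysis. A participant with no presses has no incorrect No-Go trials, so the planned contrast of correct with incorrect No-Go trials cannot be estimated for that run.
- d-prime may be added as a supporting summary, but should not replace the count.

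Section 6.1 already has task responses recorded by button-box, so no new data collection is needed. The cost is wording and the loss of a few runs from the behavioural score. Those losses could differ by arm, which is why the flagged runs should be tabulated.
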